3.1 Primary effectiveness endpoint

- Improvement in treated area appearance at 6 weeks after the last treatment as determined by a independent review.

Success criterion

The treatment will be considered successful if the appearance of Acne Vulgaris improves by at least 2 points on the 5-point Global Acne Assessment Score (GAAS) at 6 weeks follow-up compared to baseline in the study population. This will be determined by calculating the mean difference $GAAS-(\mu_d)$ between the GAAS at 6 weeks follow-up and the baseline scores in the study population. This improvement will also be further tested by two-sided Wilcoxon Signed-Ranks Test for Matched Pairs to establish that at 95% confidence level ($\alpha = 0.05$) there is a statistical significant evidence that mean difference scores obtained (μ_d) is not equal to zero.

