
Objectives
	
Primary objectives
 
 • To evaluate the efficacy of facial acne vulgaris treatment using the Venus Versa (MP)² Diamondpolar applicator in combination with the Venus Versa AC dual applicator using two Intense Pulsed Light Wavelength Bands • To evaluate the efficacy of facial acne vulgaris treatment of the Venus Versa AC dual applicator using two Intense Pulsed Light Wavelength Bands. 
Secondary objectives
 
 • To evaluate subject's assessment of improvement & satisfaction. • To evaluate subject's assessment of comfort with the treatments. • To compare the efficacy of the combination treatment and IPL treatment alone.

Hypothesis
	
Both the combination treatment and the IPL treatment will result in Acne Vulgaris improvement. Improvement will be defined as achieving improvement of at least 2 points on the 5-point Global Acne Assessment Score (GASS) at FU (6 weeks following the last treatment) as compared to baseline.

Criteria for Evaluation
	
Efficacy
 
Primary endpoint:
 
 • Acne Vulgaris improvement by at least 2 points on the Global Acne Assessment Score (GASS) from photographs 6 weeks following the last treatment - FU, as compared to baseline, based on before/after photos, as determined by up to 3 independent reviewers (dermatologists and/or plastic surgeons). 
Secondary endpoints: Subject Evaluation, Comfort & Satisfaction
 
 • Reduction of inflammatory lesions and non-inflammatory lesions as determined by investigator based on lesion count. • Improvement in subject satisfaction assessment scale with treatment outcome based on a 5-point Likert scale. • Improvement in subject self-assessment of Acne Vulgaris according to the Global Aesthetic Improvement Scale (GAIS) from photographs 6 weeks following the last

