5.2 Treatment visits

Each subject will be enrolled, randomly assigned to AC DUAL treatment (IPL alone) or Diamondpolar treatment (RF + PEMF) followed by AC Dual treatment (IPL) and scheduled for 4 treatments at 1 week intervals (\pm 5 days) and return for follow-up visit at 6 weeks after the last treatment (\pm 7 days) for evaluation of the treated areas. The duration of the entire treatment visit is approximately 40 minutes. During each visit various tasks will be performed.

The following procedures and assessments are required at the treatment visits:

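### The primary success rule, read naturally, rests on one mean GAAS change over both randomised treatments, although each has its own primary objective and both are hypothesised to improve by 2 points

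*Combined protocol and SAP*

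**What the plan says.** The Synopsis lists two primary objectives. The first concerns the Diamondpolar applicator combined with AC Dual; the second is "To evaluate the efficacy of facial acne vulgaris treatment of the Venus Versa AC dual applicator using two Intense Pulsed Light Wavelength Bands". Its hypothesis is "Both the combination treatment and the IPL treatment will result in Acne Vulgaris improvement", and "Improvement will be defined as achieving improvement of at least 2 points" on the GAAS at follow-up. Setting the two treatments against each other is a secondary objective: "To compare the efficacy of the combination treatment and IPL treatment alone".

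Under section 5.2, each subject is "randomly assigned to AC DUAL treatment (IPL alone) or Diamondpolar treatment (RF + PEMF) followed by AC Dual treatment (IPL").

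The success criterion in section 3.1 speaks of the treatment in the singular and asks for at least 2 points on the "5-point Global Acne Assessment Score (GAAS) at 6 weeks follow-up compared to baseline in the study population". On how this is judged it says "This will be determined by calculating the mean difference", again over the study population. It then adds a two-sided Wilcoxon signed-rank test at the 5% level to establish that "there is a statistical significant evidence that mean difference scores obtained" differ from zero. Section 7.4 allows a paired t-test and/or Wilcoxon test of baseline against post-treatment.

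The hypothesis is worded in two further ways. Section 1.2 states the 2-point claim for the combination only. Section 7.2 names both treatments but again refers to the study population as a whole.

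**The concern.** The objectives ask two questions and the decision rule gives one answer. If the two arms are averaged, a mean of 2 or more counts as success even when one treatment falls short of its own hypothesis. The trial could then pass with one primary objective unmet. The secondary comparison in sections 3.2, 3.6 and 6 would show a difference between the arms, but it applies no 2-point rule to either.

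If the sponsor does intend an arm-by-arm reading, leaving it unstated is still a problem, because the choice could be made after the results are known. Nor do the planned tests supply the missing verdict: their null value is zero, not 2.

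**Working it through.** **Inputs from the documents.** Threshold: mean change of at least 2 (section 3.1). Two randomised arms, ratio not given (section 5.2). Up to 50 subjects enrolled, with 20 completers targeted on the amended parameters (Synopsis). Section 7.3 gives no SD, effect size or power, so there is no sample-size figure to reproduce.

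**Assumptions.** 1:1 allocation, hence 25 per arm (from 50) or 10 per arm (from 20). SD of the GAAS change 0.7 to 1.3. True arm means as shown. Normal approximation for the means.

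**Step 1: averaging.** With equal arms the pooled mean is (m1 + m2)/2. Means of 2.3 and 1.7 give (2.3 + 1.7)/2 = 2.0; means of 2.2 and 1.5 give 1.85.

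**Step 2: chance of passing.** P(observed mean ≥ 2) = 1 − Φ((2 − μ)/SE), with SE = SD/√n for an arm and SD/√(2n) pooled. Example with SD 1.0, n = 25 and weaker mean 1.7: arm SE = 0.20, z = 0.3/0.20 = 1.5, so the weaker arm passes 6.7% of the time. The pooled z is 0, so the pooled rule passes 50%.

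**Step 3: the strong arm carries the weak one.** P(pooled ≥ 2 and weaker arm < 2) = Φ(z_w) − Φ₂(z_p, z_w; ρ), where z_w and z_p are the weaker-arm and pooled z values and ρ = 1/√2 is the correlation between the pooled mean and one arm's mean. In the example this is 43.5%. As a check, it must lie between 50% − 6.7% = 43.3% and 50%.

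Ranges below run over SD 0.7 to 1.3.

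| True means | Per arm | Pooled rule passes | Weaker arm alone reaches 2 | Pooled passes, weaker arm below 2 |
|---|---|---|---|---|
| 2.3 and 1.7 | 25 | 50% | 1.6% to 12% | 38% to 48% |
| 2.3 and 1.7 | 10 | 50% | 8.8% to 23% | 29% to 42% |
| 2.2 and 1.5 | 25 | 6.5% to 21% | 0.02% to 2.7% | about 6% to 18% |
| 2.2 and 1.5 | 10 | 17% to 30% | 1.2% to 11% | 16% to 21% |

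**Step 4: does the short scale change this?** Restrict changes to whole points from 0 to 3, fit p(x) ∝ exp(ax + bx²) to each mean and SD (0.7 to 1.0), and convolve exactly. For 2.3 and 1.7 the last column becomes 46% to 52% (25 per arm) and 36% to 45% (10 per arm). The result does not depend on the normal approximation.

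**Step 5: the test against zero.** Suppose the true mean change is 1 point, half the criterion. A two-sided paired t-test at 5%, with noncentrality √n × 1/SD, has power of 90% to over 99.9% at n = 20 and over 99.9% at n = 50. A significant result is therefore expected well below the threshold.

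**Step 6: intervals.** Section 3.1's 95% confidence level describes the test's alpha. Section 7.4 lists mean, SD, median and other descriptive statistics. Neither names an interval for the mean change.

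**The case against.** The strongest reply is that pooling is inferred. No sentence says the arms are combined. The singular treatment in section 3.1 could be taken as each treatment in turn, section 3.6 speaks of primary endpoints in the plural, and section 3.2 requires the arms to be compared on the primary endpoint, so arm-level results must exist. A sponsor could apply the rule per arm without contradicting any sentence. This stands as a limit on certainty: a reader might infer that the plan expressly pools the arms, and the documents do not support that. It does not remove the problem, because no passage directs the per-arm reading and section 3.1 ties both the criterion and the mean to the study population.

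Second, the choice of scenario matters. Means of 2.3 and 1.7 average exactly 2, which by itself forces the 50% pooled pass rate; that rate is not a property of the design. The 2.2 and 1.5 rows are shown for this reason. Stronger-arm means above 2 may also be hard to reach, since mild acne is eligible and leaves less room to improve. The documents do not give the scale's grade definitions, so this cannot be settled.

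Third, a reader might infer that the sponsor offers the test against zero as proof of a 2-point improvement. Section 3.1 does not: it presents the test as a further check for change. The fair statement is only that the test does not bear on the threshold.

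Fourth, section 7.3 calls this a pilot, section 7.1 promises a final plan before data lock, and an interval can be derived from the planned mean and SD. These points limit the seriousness and make correction easy. They do not supply a rule for each objective.

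**Conclusion.** Wrong as written, with moderate confidence because pooling is the natural reading and not an express instruction. The Synopsis, section 1.2, section 3.1 and section 7.2 do not agree on what must improve by 2 points. On the natural reading, success can be declared while one of the two primary objectives fails. How often depends on true means, SD and allocation that the documents do not give: often when the two true means average about 2, and less often, though not negligibly, when they average 1.85. No planned test or interval fills the gap. It should be corrected before data lock; in a pilot it is not a fatal defect.

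**What to change.** Change sections 3.1 and 7.4, and carry the change into the final plan that section 7.1 promises before data lock:

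1. Apply the 2-point mean rule separately to each randomised arm, with one verdict per primary objective. Claim success for both treatments only if both arms meet it.
2. Align the hypothesis in sections 1.2 and 7.2 with the Synopsis.
3. Report each arm's mean GAAS change with a 95% CI.
4. Describe the test against zero only as evidence of change from baseline.

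No new data are needed. The costs, under the same assumptions, should be stated:

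- **Wide intervals.** Half-width = t(0.975, n − 1) × SD/√n, with t = 2.262 at n = 10 and 2.064 at n = 25: 0.50 to 0.93 at 10 per arm, 0.29 to 0.54 at 25 per arm.
- **A harder joint claim.** If both true means are 2.3, the chance that both arms pass is p², where p is one arm's chance. At 10 per arm this is 59% to 83% (0.767² to 0.912²), against 85% to 97% pooled. At 25 per arm it is 77% to 97%, against 95% to 99.9%.
- **Two chances of a single-arm claim.** If both true means are 1.7, the chance that at least one arm passes is 1 − (1 − p)². At 10 per arm this is 17% to 41%, against 2.8% to 15% pooled. At 25 per arm it is 3.2% to 23%, against 0.1% to 5.1%.

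The rule also remains a point-estimate rule: an arm whose true mean is exactly 2 passes about half the time. For both of these last reasons each verdict should be shown with its interval.

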3.2 Secondary effectiveness endpoints

- Reduction of inflammatory lesions and non-inflammatory lesions.
- Subject Improvement assessment in treated area appearance at 6 weeks after the last treatment compared to baseline using the Global Aesthetic Improvement Scale (GAIS).
- Subject assessment of pain and discomfort associated with treatments using a 100 mm Visual Analogue Scale (VAS), were 0 is "no pain" and 10 is "intolerable pain".
- Subject's satisfaction with treatment outcome based on a 5-point Likert scale.
- Subject improvement assessment of "quality of life" using QOL Questionnaire.
- Comparison of the two treatments for the primary and secondary endpoints.

3.3 Safety

- Safety will be evaluated based on the number and type of any adverse event recorded throughout the study. Adverse events will be reported and categorized based on severity and device-relatedness. In addition, immediate response following treatment associated with various settings (e.g., erythema, edema, purpura, etc.), although expected results of treatment that are not considered adverse events, will be collected and reported for purposes of completeness. Information will also be captured on the intensity of response and the time required for resolution.

3.4 Study duration:

Duration of subject's participation: Up to 11 weeks from enrollment to termination (see Figure 1).

Study duration for entire study sample: Estimated to be 16 months from enrollment of first subject to the termination of the last. This is based on estimate of 8 months for recruitment + 2 months subject participation + 1 months collecting data.

Figure 1: Subject Participation

Time Intervals		1 week	1 week	1 week	1 week	6 weeks
	Enrollment	Treatment 1	Treatment 2	Treatment 3	Treatment 4	Follow-up
Timeline	Screening	Week 1	Week 2	Week 3	Week 4	Week 10

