procedure. At the first treatment visit, the investigator will collect demographic and medical information and perform 3 test spots to evaluate skin sensitivity and choose appropriate presets. Subjects with skin type IV-V will be monitored 48-96 hours after the test spot for their skin reaction. Subjects that demonstrate excessive skin reaction to the test spot will be withdrawn from the study and will not be included in the study efficacy population or in the safety analysis since study treatment has not occurred. Should a subject (or the subject's legally authorized representative) decide to voluntarily withdraw, all efforts will be made to collect and report the final visit observations, and the reasons for withdrawal, as thoroughly and timely as possible. Withdrawals will be documented in the CRF and reported to local institutional review board (IRB) or ethical committees as required. The first treatment visit may occur on the same day as the screening visit but can be scheduled up to 30 days after the screening.

The duration of the treatment session will be approximately 40 minutes depending on the treated area size. Expected immediate response includes temporary mild to moderate erythema and/or edema. Skin safety assessments will be conducted by the investigator after each treatment session and at follow-up visits. Photography will be conducted at baseline, the beginning of last visit and at FU. The level of the subject's discomfort will be documented at the end of each treatment session. Subject satisfaction will be evaluated at FU. Evaluation by up to 3 independent reviewers will be based on before/after pictures of the baseline, before the last treatment and at the 6 week follow up visit using GAAS.

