3.5 Schedule of Times and Events

The following table provides a summary of the required study visits and the procedures and assessments to be performed at each visit. Details of the procedures and assessments will be described subsequently in the protocol.

Table 1: Study Procedures - CS2715

Tx=Treatment; FU=Follow Up

Visit#	Visit #1	Visit #2	Visit #3	Visit #4	Visit #5	Visit #6
Study Activities	Screening & Test spot	Tx1	Tx2	Tx3	Tx4	FU
Timing (see Figure 1)		0-7 days post given ICF	1 week + 5 days post 1 st TX	2 weeks + 5 days post 1 st TX	3 weeks + 5 days post 1 st TX	6 weeks + 7 days after last Tx
Informed Consent	X					
Eligibility assessment	X					
Demographic information	X					
Medical/surgical history	X					
Physical examination	X					
Urine pregnancy test	X					X
Test spots	X					
Photographs		X			X	X
Lesion Count (FACE)	X	X	X	X	X	X
Treatment		X	X	X	X	
Immediate/short term response		X	X	X	X	
Subjects discomfort assessment (VAS)		X	X	X	X	
Subject improvement evaluation using GAIS						X
Subject satisfaction assessment scale (5-point Likert scale)						X
Subject improvement assessment of "quality of life" using QOL Questionnaire	X		X	X	X	X
Independent reviewer improvement evaluation using GAAS						X
Adverse events		X	X	X	X	X
Concomitant medications		X	X	X	X	X

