5.2.3 Post-treatment Instructions

5.2.3.1 *Subject discomfort evaluation*

The subject will record their assessment of pain on a 100 mm VAS CRF page immediately after each treatment which will be considered to be a source document.

Subjects will be asked to directly complete the CRF Acne Related Quality of Life Questionnaire worksheet which will be considered to be a source document after Tx 2, Tx 4 and Tx 4.

5.2.3.2 *Skin safety – immediate response after procedure*

- Local (dermal) tolerability examination (only on the face) will be performed immediately following treatment at the time-points given in the Study Visit Table and will include assessments of pain during treatment, hemorrhage, burn, erythema, edema or other reactions. All tolerability assessments must be completed by the same person throughout the study whenever possible. Local tolerability on the face will be rated as none, mild, moderate, or severe.
- Cold air or cold, wet but not frozen gauze pads may be placed on the treated area for post treatment cooling.
- Shortly after treatment, a topical emollient should be applied over the areas, without dressings of any sort.
- Subjects should remain in the research setting at least 30 minutes after treatment in order to ensure their well-being.

5.2.3.3 *Home instructions*

- On the night following treatment, subjects should generally avoid hot water, cleanse their skin gently with tepid water, and hydrate the skin with a suitable moisturizer. Aloe Vera gel, Biafin cream, or any other anti-burn cream may be applied as well. Threolone ointment or its equivalents may be applied if any damage occurred to the skin or as a preventative measure. It is important to avoid mechanical damage to the treated area and it should not be rubbed, scratched or picked.
- If necessary, over-the-counter analgesics may be taken for pain management. It should be noted, however, that subjects should be instructed to use only acetaminophen-based ones, such as Extra Strength Tylenol®. Non-steroidal anti-inflammatory drugs (NSAIDS), such as Advil®, may affect microvasculature and hence may make the post-treatment erythema disappear artificially, thus hindering our ability to follow its natural resolution, which is part of the study's objectives.

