6.3 Safety

6.3.1 Immediate/short term response

Immediate response (pain during treatment, hemorrhage, burn, erythema, edema, etc.) of the skin will be assessed by the principal investigator or qualified designate within 30 minutes post treatment by a 4 level scale: (0) None / (1) Mild / (2) Moderate / (3) Severe.

Short-term response (dryness, sloughing/flaking etc.) of the skin may develop following each treatment which is expected to resolve within several days. These responses are not considered as adverse events since they are expected outcomes related to the treatment. However, if the principal investigator determines that the severity or duration of the short-term response is abnormal, then it will be documented as an adverse event. Again, for purposes of completeness, this information will be documented in the relevant CRF of the next visit.

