8.1.5 Anticipated Outcome Related Adverse Events

Anticipated adverse events in this study may include: Irritation, blistering, temporary skin color changes, burns, excessive edema or erythema (excessive consider as edema or erythema that do not resolve within 2-3 days), infection, PIH (post inflammatory hyperpigmentation) and scarring. If any antibiotic ointment will be required during the study it will be provided by the study doctor at no cost.

Any anticipated AE that occurs at any time during or after the use of the study device must be reported by the Investigator to Venus Concept. If the anticipated AE, in the opinion of Venus Concept or the Investigator, is likely to affect the safety of the subjects or the conduct of the study, the IRB/ Helsinki/ other ethic committee will be notified of the effect within 10 working days after Venus Concept first receives notice of it. In this study if an adverse event of PIH occurs during the course of the 3 month follow-up period the Investigator will continue following the subject until the PIH is resolved or up to 3 months following the last treatment, whichever comes first.

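### Time to resolution of expected skin reactions is promised, but nothing is scheduled between the 30-minute score and the next visit, and Table 1 conflicts with the text on recording the response at follow-up

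*Combined protocol and SAP*

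**What the plan says.** All references are to the combined protocol and SAP.

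- **The promise.** Section 3.3 says immediate responses such as erythema, edema and purpura are expected and are not adverse events, but will still be reported. It adds: "Information will also be captured on the intensity of response and the time required for resolution".
- **A restriction made for its sake.** Section 5.2.3.3 limits over-the-counter analgesics to acetaminophen because NSAIDs could make erythema fade artificially, "thus hindering our ability to follow its natural resolution, which is part of the study's objectives".
- **The immediate score.** Under section 6.3.1 the immediate response "will be assessed by the principal investigator or qualified designate within 30 minutes post treatment by a 4 level scale".
- **The later record.** The same section says of short-term responses that "this information will be documented in the relevant CRF of the next visit".
- **Table 1 (section 3.5).** The row "Immediate/short term response" is marked at Tx1 to Tx4 and blank at follow-up (Visit 6). The row "Adverse events" is marked at Tx1 to Tx4 and at follow-up.
- **Section 3 text.** "Skin safety assessments will be conducted by the investigator after each treatment session and at follow-up visits".
- **Section 5.3.** The follow-up procedures cover photography, GAAS and lesion count, and subject ratings. No skin-response assessment is listed.
- **The boundary for an anticipated adverse event.** Section 8.1.5 qualifies excessive edema or erythema: "excessive consider as edema or erythema that do not resolve within 2-3 days".

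**The concern.** Time to resolution can be measured only if someone looks, or the subject notes a date, at about the time the reaction clears. The plan fixes one look within 30 minutes and the next at the following visit. Section 5.2.1.3 tells subjects to expect purpura to clear within several days, so much of what is to be timed would begin and end between the two looks.

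Two things are at stake. First, a promised safety description, for which subjects accept an analgesic restriction, may not be obtainable in usable form. Second, the section 8.1.5 boundary between an expected reaction and an anticipated adverse event lies inside the same gap. The safety evaluation is the number and type of adverse events, so the quality of that classification bears on what is counted.

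Separately, sites reading different parts of the protocol would do different things at follow-up about the response to Tx4.

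**Working it through.** The plan gives no figure to reproduce. The check is visit-window arithmetic followed by a comparison of sections.

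**Inputs.** Immediate score: within 30 minutes (6.3.1). Treatment interval: 1 week, plus or minus 5 days (5.2). Follow-up: 6 weeks after the last treatment, plus or minus 7 days (5.2). Cut-off for excessive erythema or edema: 2-3 days (8.1.5).

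**Gap from a treatment to the next scheduled look, in days**

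| Gap | Arithmetic | Result |
|---|---|---|
| Tx1-Tx3, nominal | 7 | 7 |
| Tx1-Tx3, window on each interval | 7 − 5 to 7 + 5 | 2 to 12 |
| Upper limit if visits are instead anchored to Tx1, plus or minus 5 | (14 + 5) − (7 − 5) | 17 |
| Tx4 to follow-up, nominal | 6 × 7 | 42 |
| Tx4 to follow-up, with window | 42 − 7 to 42 + 7 | 35 to 49 |

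Table 1 prints the windows with a plus sign only, which may be an artefact of text extraction. Read literally, it gives 42 to 49 days after Tx4, and the conclusion is the same.

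**Distance of the next look past day 3**

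- After Tx1-Tx3, nominal: 7 − 3 = 4 days.
- After Tx4, nominal: 42 − 3 = 39 days; range 35 − 3 = 32 to 49 − 3 = 46 days.

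A scheduled look on day 2 or 3 is possible after Tx1-Tx3 only at the early edge of the window. It is never possible after Tx4.

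**What the scheduled looks can establish.** If a reaction is present at 30 minutes and gone at the next visit, direct observation shows only that it ended somewhere in between: within about 7 days after Tx1-Tx3, within about 42 days after Tx4. Anything finer comes from the subject's memory.

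**Where a resolution date is required.** Section 8.1 asks for onset and resolution dates for adverse events. Section 3.3 places the expected reactions outside that class, so the reactions whose duration is promised are not covered by that requirement. Section 6.3.1 sends short-term responses to the next visit's CRF, but its examples are dryness and flaking. Erythema, the reaction named in section 5.2.3.3, is listed there only under the 30-minute assessment.

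**Recording after Tx4.**

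| Source | Skin response at follow-up? |
|---|---|
| Section 3 | Yes |
| Section 6.3.1 | Yes for short-term response, since follow-up is the next visit after Tx4 |
| Table 1, response row | No mark |
| Section 5.3 | Not listed |

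**When a reaction becomes an adverse event.** Section 8.1.5 uses 2-3 days, itself a range. Section 6.3.1 expects short-term responses to clear within several days and leaves escalation to the investigator's view of abnormal severity or duration. Section 5.2.1.3 asks subjects to report symptoms that outlast several days. These are three different triggers.

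**The case against.** The strongest reply is that the protocol has more cover than the response row suggests. Table 1 has a follow-up column with adverse events marked. Sections 3 and 6.3.1 both provide for recording at follow-up, and section 3.5 describes the table as a summary. Subjects are told to report persisting symptoms (5.2.1.3), unscheduled visits are allowed for adverse events (5.4), and every adverse event gets a resolution date (8.1). Intensity is scored at 30 minutes, so that half of the promise is met. The data are collected for completeness in a pilot study, and the CRF is not among the documents and may ask for a date.

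Much of this stands, and it rules out several inferences a reader might draw:

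- **That the Tx4 response is lost, or that one session in four has no record.** Sections 3 and 6.3.1 route it to follow-up. The supportable finding is a contradiction with Table 1 and, on the text's reading, recall after 5 to 7 weeks.
- **That adverse event rates or durations will be understated.** Recall error can run either way, and the documents show no direction.
- **That a difference between the two treatments in reaction duration could not be seen.** It would be poorly measured, and section 3.2 plans the comparison for the primary and secondary endpoints, of which duration is not one.
- **That reactions go wholly unobserved.** They are not observed by any scheduled assessment in the gap; self-report and unscheduled visits remain.

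These channels do not close the gap. Self-report is prompted at several days rather than 2-3, unscheduled visits depend on an adverse event having been recognised, and neither gives a resolution time for a reaction that never becomes one.

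**Conclusion.** The point holds in limited form. As written, the plan does not provide a usable resolution time for expected reactions, although section 3.3 promises one. The next scheduled look is nominally 4 days past the 3-day mark after Tx1-Tx3 and 32 to 46 days past it after Tx4. Table 1 and section 5.3 disagree with sections 3 and 6.3.1 on the skin response at follow-up, so collection after Tx4 may vary by site.

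This should be corrected, but it does not touch the primary endpoint. The conclusion assumes that the blank follow-up cell is in the source table, and that no CRF field or site procedure outside the documents collects dated resolution. If such a field exists, the recall problem remains unless it is completed close to the event.

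**What to change.** 1. In Table 1, mark the immediate/short-term response row at Visit 6, and add the assessment to section 5.3, so that both agree with sections 3 and 6.3.1.
2. After each treatment, give the subject a one-page dated card on which to mark each day whether erythema, edema, purpura and flaking are present, until clear. Collect it at the next visit (follow-up for Tx4), and derive time to resolution from the dates. If the sponsor does not want this, withdraw the resolution-time statement in section 3.3 and revisit the rationale in section 5.2.3.3 that depends on it.
3. Reconcile the wording in sections 5.2.1.3, 6.3.1 and 8.1.5 on when a reaction becomes an adverse event, so that one stated rule can be applied to dated information. Which rule is a matter for the sponsor and investigators.

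Cost: one table cell, a line in section 5.3, a one-page worksheet, and at most 50 × 4 = 200 cards to review and enter. Subjects take on a small task for a few days after each session. No extra visit or clinical procedure is needed, but the amendment requires ethics committee approval under section 9.7.
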